5.1.3 Definitions

5.1.3.1 Baseline

For clinic visit based endpoints, baseline is defined as the last record or measure collected prior to the first dose of IMP.

For IVRS based endpoints, baseline will include all available data from the day of Visit 2 to Day 1 of the blinded phase.

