5.1.3.4 Treatment Period

The treatment period of the double-blind phase is defined as Day 1 to Day 113.

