5.1.3.5 Titration Period

The titration period of the double-blind phase is defined as Day 1 to Day 28.

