5.1.3.6 Maintenance Period

The maintenance period of the double-blind phase is defined as Day 29 to Day 113.

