Where X corresponds to the treatment period estimate, or GWP42003-P ratio, and Y corresponds to the baseline period estimate, or placebo arm ratio.

Primary efficacy analysis will be performed using the ITT analysis set.

TSC-associated seizure frequency (28-day average) and percentage change in seizure frequency will also be presented using summary statistics. Percentage change from baseline in TSC-associated seizure frequency will be calculated as:

$$((\text{Frequency during the treatment period} - \text{Frequency during baseline}) \div \text{Frequency during baseline}) \times 100$$

The frequency during each period will be based on 28 day averages and calculated as:

$$(\text{Number of seizures in the period} \div \text{Number of reported days in IVRS in the period}) \times 28$$

For the TSC-associated seizure endpoints only, if patients are randomized with no TSC-associated seizures during the baseline period then the percentage change from baseline will be calculated as:

$$(\text{Frequency during the treatment period} + 1) \times 100$$

Open-label Extension:

The primary endpoint for the OLE is the safety of GWP42003-P, evaluated by assessing the incidence, type and severity of AEs. Data will be presented as per Section 5.6.2.

However, percentage change from baseline in TSC-associated seizure frequency is considered a key secondary endpoint for the OLE.

In the OLE, seizures are recorded on a weekly basis rather than daily. Caregivers/patients are expected to call the IVRS system to record the number of seizure subtypes experienced every 7 days during the OLE. TSC-associated seizure frequency per 28 days will be calculated for each of the periods described in Section 5.5.1. All calls that take place during the period in question will contribute to the calculation of the average number of seizures per day in that period only.

The average number of seizures per day in the period will be calculated as the average of:

$$\text{Number of seizures reported} \div \text{Number of days since last IVRS call}$$

The number of days since the last call will be calculated as follows, and is dependent on whether the call took place <7, 7 or >7 days after the previous call (or after the date of OLE Day 1 in the case of the first call in the first period):

- If the call takes place exactly 7 days after the previous call, then the number of days since the last call will be 7.

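### Two derivation rules are wrong as written, with limited effect: no seizures in either period scores as a 100% increase, and Day 1 is counted in both baseline and treatment

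*SAP*

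**What the plan says.** **Zero baseline.** Section 5.5.2 of the SAP begins its general rule with "Percentage change from baseline in TSC-associated seizure frequency will be calculated as" and then gives (treatment frequency - baseline frequency) / baseline frequency x 100, so positive values are increases. For TSC-associated seizure endpoints it makes one exception: "if patients are randomized with no TSC-associated seizures during the baseline period then the percentage change from baseline will be calculated as" (treatment frequency + 1) x 100.

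**Day 1.** Section 5.1.3.1 states: "For IVRS based endpoints, baseline will include all available data from the day of Visit 2 to Day 1 of the blinded phase". Section 5.1.3.4 states: "The treatment period of the double-blind phase is defined as Day 1 to Day 113". No section removes Day 1 from either window. Section 3.1 describes a 4-week baseline that is completed before randomization, and Section 5.1.2 makes Day 1 the first day of treatment.

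**The concern.** A rule for an undefined quantity should at least score an unchanged patient as unchanged. This one gives a patient without a single seizure the same value as a patient whose seizures doubled. The percentage change feeds the descriptive summary in Section 5.5.2, the Wilcoxon, rank-ANCOVA and ANCOVA sensitivity analyses in Section 5.5.2.1, and the change categories and cumulative plots in Section 5.5.3.2.1. Those categories include one for an increase of 0 to 25%, where an unchanged patient belongs. The rule puts that patient in the worst category instead.

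The Day 1 overlap is a different matter, and it does touch the primary analysis. The model in Section 5.5.2 takes one count and one log-days offset per period. If Day 1 lies in both periods, the same day and the same seizures appear on both sides of the treatment-to-baseline ratio.

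**Working it through.** **A. Zero-baseline rule** (f = treatment frequency per 28 days, baseline = 0)

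1. SAP rule at f = 0: (0 + 1) x 100 = +100%. A patient going from 8 to 16 scores (16 - 8) / 8 x 100 = +100%, the same value.
2. The SAP treats zeros differently elsewhere. The log-rate fallback (Section 5.5.2) and the log-transformed ANCOVA (Section 5.5.2.1) add 1 in both periods. Assuming that convention here, the general formula gives ((f + 1) - (0 + 1)) / (0 + 1) x 100 = 100f.

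| f | SAP rule | Add 1 to both periods |
|---|---|---|
| 0 | +100% | 0% |
| 1 | +200% | +100% |
| 4 | +500% | +400% |

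3. Responder status: a 50% responder needs a change of -50% or lower. With a zero baseline, the SAP rule gives +100% or more and the alternative gives 0% or more. The patient is a non-responder under both.
4. Effect on an arm mean: one patient shifted by 100 points in an arm of 70 moves it by 100 / 70 = 1.4 points. With the planning SD of 60% (Section 3.2), the standard error of an arm mean is 60 / sqrt(70) = 7.2 points, so the shift is about 0.2 standard errors per patient.
5. Effect on ranks, assuming normality with the planning means of -15% and -50%: +100% lies (100 + 15) / 60 = 1.9 SD above the placebo mean and (100 + 50) / 60 = 2.5 SD above the active mean, near the 97th and 99th percentiles. A score of 0% lies 0.25 and 0.83 SD above, near the 60th and 80th.

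**B. Day 1 overlap**

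1. How the SAP uses the word to: "The titration period of the double-blind phase is defined as Day 1 to Day 28" and "The maintenance period of the double-blind phase is defined as Day 29 to Day 113". These are 28 + 85 = 113 days. The imputation section (5.5.2.1.1) uses 14-day blocks with a last block of 15 days: 7 x 14 + 15 = 113. End days are therefore included, and Day 1 belongs to treatment.
2. Visit 2 is Day -28 (Table 2) and there is no Day 0 (Section 5.1.2). Day -28 to Day 1 is 29 days; Day -28 to Day -1 is 28 days, the 4 weeks of Section 3.1. The shared day is Day 1: 1/29 = 3.4% of baseline and 1/113 = 0.9% of treatment.
3. Size: set the baseline rate to 1, the treatment rate to r and the Day 1 rate to x, with every day reported. With overlap, the ratio is [(x + 112r) / 113] / [(28 + x) / 29]. With disjoint windows, the denominator is 1. Take r = 0.50 and 0.85 from the planning reductions of 50% and 15%.

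| Day 1 rate | Quantity | Overlap | Disjoint |
|---|---|---|---|
| Treatment rate (x = r) | Arm with r = 0.50 | 0.509 | 0.500 |
| | Arm with r = 0.85 | 0.854 | 0.850 |
| | Between-arm ratio | 0.595 | 0.588 |
| Baseline rate (x = 1) | Between-arm ratio | 0.593 | 0.593 |

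**C. How the two interact.** A patient whose only baseline seizure falls on Day 1 escapes the zero-baseline rule under the present window and falls under it once baseline ends at Day -1. If that is also the only treatment-period seizure, the printed windows give 29/113 - 1 = -74%, a responder; disjoint windows give a zero baseline and a non-responder. This case should be rare, but it is a route by which the window, unlike the zero-baseline rule, could alter responder status.

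**The case against.** - **The primary result is not at stake through the zero-baseline rule.** A reader might infer that it is, because the rule stands in the primary endpoint section. The documents do not support that: the primary model uses counts and reported days, and percentage change never enters it. The first key secondary endpoint is also untouched by the rule. This stands in full.
- **Percentage change from zero is undefined, so any rule is a convention.** A reader might infer that every zero-baseline patient is scored exactly 100 points too high. That holds only under the add-1 convention, which the SAP specifies for its log-scale analyses and log-rate fallback, not for percentage change. What the text does support is narrower: a patient with no seizures in either period should not score +100%. A deliberate penalty for new seizures, which the SAP does not claim, could not explain penalizing a patient who has none.
- **The rule may rarely apply, and rank methods limit its influence.** The clause is conditional and one patient moves little. But ranks do not neutralize the error, because +100% sits near the top of the expected distribution.
- **The baseline end point may have meant up to Day 1.** Section 3.1 supports that intention. The wording does not, since the SAP's other period definitions include their end day.
- **The overlap might be read as favouring the drug.** It does not: the rule is the same in every arm, and where it has an effect in these calculations it pulls the ratios towards 1. An unchanged ratio is also plausible, since the first dose is taken in clinic that day and escalation has only begun.

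**Conclusion.** Both rules are wrong as written, and both effects are limited.

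The zero-baseline rule misclassifies any patient with no seizures in either period. The damage is confined to descriptive output, three sensitivity analyses, the change categories and the cumulative plots. Its total size depends on a number that the SAP does not give; per patient it is about 1.4 points on an arm mean of 70.

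The Day 1 overlap does enter the primary model. In the worked example it changes an arm's ratio by under 2% (0.500 to 0.509) and the between-arm ratio by about 1% (0.588 to 0.595), in the conservative direction. These figures assume constant rates within each period, full diary reporting and the planning reductions. Neither defect is a reason to doubt the primary conclusion, but both should be corrected because they are specific and cheap to mend.

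**What to change.** 1. **Section 5.5.2:** set the percentage change to 0% when both periods have no TSC-associated seizures. For a zero baseline with seizures on treatment, either keep a convention that is stated and justified as such, or use treatment frequency x 100.
2. **Section 5.1.3.1:** define the diary baseline as the day of Visit 2 to Day -1, with Day 1 in the treatment period only. Apply this before the zero-baseline rule, because it can change who has a zero baseline.
3. **Reporting:** state the number of zero-baseline patients by arm, and how many of them also had no seizures on treatment.

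The cost is two derivation lines and reruns of the outputs that depend on them, including the primary model for the window change. There are two drawbacks. With treatment frequency x 100, a patient with one new seizure in 113 reported days has f = 28/113 = 0.248, or +24.8%, and lands in the 0 to 25% increase category although seizures newly appeared; this should be noted if that option is chosen. Also, the addendum (Section 2.3.3) already compares withdrawal between arms, so a change made now is post hoc. It should be labelled as such and shown beside the results under the printed rules.

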5.5.2.1 Sensitivity Analyses for the Primary Efficacy Endpoint

Blinded Phase:

The following sensitivity analyses will be conducted for the primary endpoint of the blinded phase:

- Primary endpoint analysis repeated using the PP analysis set.
- Wilcoxon rank-sum test on percentage change from baseline in TSC-associated seizure frequency during the treatment period. An estimate of the median differences between each GWP42003-P arm and placebo, together with approximate 95% CIs, will be calculated using the Hodges–Lehmann approach.
- A rank analysis of covariance (ANCOVA) on percentage change from baseline in TSC-associated seizure frequency during the treatment period.

The ranks of the percentage change from baseline and the baseline TSC-associated seizure frequency will be calculated. The rank of the percentage change from baseline will then be analyzed using an ANCOVA model with the rank of the baseline TSC-associated seizure frequency and stratified age group as covariates and treatment arm as a fixed factor. The estimated least squares means, treatment differences, together with the 95% CIs and p-values will be presented.

- ANCOVA of log transformed TSC-associated seizure frequency during the treatment period.

The TSC-associated seizure frequency during the treatment period and the baseline TSC-associated seizure frequency will be log transformed prior to analysis. The log transformed TSC-associated seizure frequency during the treatment period will then be analyzed using an ANCOVA model with the log transformed baseline TSC-associated seizure frequency and stratified age group as covariates and treatment arm as a fixed factor. The back transformed estimated treatment ratios, together with the 95% CIs and p-values will be presented.

If there are any patients with no TSC-associated seizures during the baseline or treatment periods, then 1 will be added to the TSC-associated seizure frequency for all patients prior to log transformation.

- ANCOVA on percentage change from baseline in TSC-associated seizure frequency during the treatment period including baseline and stratified age group as covariates

and treatment arm as a fixed factor. The estimated least squares means, treatment differences, together with the 95% CIs and p-values will be presented.

- Primary endpoint analysis repeated using the maintenance period (see Section 5.1.3.6) rather than the treatment period.

This analysis will include only patients who have at least 7 days of seizure data within the maintenance period.

- Primary endpoint analysis repeated using the titration period (see Section 5.1.3.5) each 4 weeks of the maintenance period (Week 1 to 4, Week 5 to 8 and Week 9 to 12 of the 12-week maintenance period).
These analyses will include only patients who have at least 7 days of seizure data within each corresponding 4 week period.
- Primary endpoint analysis repeated using the worst case of last observation carried forward (LOCF), next observation carried backward (NOCB) and the mean from the non-missing data for each patient (rounded up to the nearest integer) to impute missing data arising from unreported days in IVRS during the treatment period only (not the baseline period).

Any intermittent missing data for the number of TSC-associated seizures arising from unreported days in IVRS will be imputed using the worst (highest number of seizures) of the following for each patient: LOCF, NOCB and the mean daily number of seizures during the treatment period (rounded up to the nearest integer) based on using non-missing data:

$$\text{Number of seizures} \div \text{Number of reported days in IVRS}$$

- Primary endpoint analysis repeated using multiple imputation (MI) to impute data under the Missing Not at Random (MNAR) assumption (see Section 5.5.2.1.1).

Open-label Extension:

Open-label summaries will be repeated with the inclusion of an LOCF imputation step, which is described in the following steps:

- If a patient has valid data for ≥ 1 consecutive periods from and inclusive of the first period but only missing periods thereafter, then imputation of the missing period(s) will be carried out using the last 12 weeks of valid data (see Section 5.1.3.3).
- If a patient has intermittent missing periods (i.e. ≥ 1 missing period that falls after a populated period 1 and before subsequent populated periods), then the missing period(s) will be imputed with the closest earlier non-missing period of data.
- If the patient has ≥ 1 consecutive periods of missing data from and inclusive of the first period then no imputation will occur and data from the patient will be excluded from any LOCF presentations.

5.5.2.1.1 Sensitivity Analysis of Missing Data

Missing data in this trial could potentially arise from the mechanism of MNAR. Hence, a sensitivity analysis is required to assess the potential impact that missing data under the mechanism of MNAR may have on the estimated results for the primary endpoint.

To facilitate multiple imputation techniques for missing data due to patients who withdraw from the treatment period, it is necessary to divide the treatment period into smaller periods for which missing seizure data can be imputed. Hence, sensitivity analysis of the primary endpoint will be carried out based on periods corresponding to each 14 days of the

treatment period, by multiple imputations on the average daily TSC-associated seizure frequency. The final period will consist of 15 days to include Day 113, where applicable. Following imputation, the imputed periods will be recombined for each patient in order to repeat the primary analysis.

For each 14 calendar days of the treatment period (15 days for the final period), the average daily TSC-associated seizure frequency will be calculated as:

$$\left(\frac{\text{Number of TSC-associated seizures in the period}}{\text{Number of reported days in IVRS in the period}} \right)$$

For patients with <6 days in a period, the frequency will be set to missing and will be imputed as part of this analysis.

For intermittent missing data, in which subjects have missing values for intermediate periods but have available data at subsequent periods, imputation will be based on the MCMC methodology. Assumptions underlying this partial imputation step are that patients will follow a similar outcome trajectory as patients in their respective treatment arm that have complete data. Intermittent missing values will be imputed using the MCMC method in PROC MI with an IMPUTE=MONOTONE statement for 200 times for each treatment arm separately. To avoid negative results, a minimum of 0 will be specified in the PROC MI statement. As a result, missing intermediate visits will be imputed and the resulting 200 partially imputed datasets will have a monotone missing pattern.

The remaining monotone missing data will then be imputed using predictive mean matching in which missing observations are imputed with an observed value from another patient whose predicated value is close to the predicated value of the patient with the missing observation. The predictive mean matching is performed using the steps below, in which imputation will be carried out on each of the 200 imputed datasets using the SAS MI procedure (with the 200 imputed datasets included in the 'BY' statement of the MI procedure):

Step 1 – Missing at random (MAR) based multiple imputation for the placebo arm:

- Monotone missing data under the MAR assumption at period t will be imputed using predictive mean matching method from the observed daily TSC-associated seizure frequency at baseline and at each period up to period t (in chronological order)
- The imputation will be realized using the MI procedure with the 'MONOTONE REGPMM' option.
- The imputation model will include baseline daily TSC-associated seizure frequency and each period up to period t (in chronological order).

Step 2 – MNAR based multiple imputation for the GWP42003-P arms (MNAR is assumed for missing values resulting from discontinuation due to any reason or any other monotone missing data):

- With the data imputed from Step 1, monotone missing data under the MNAR at period t will be imputed using predictive mean matching method.
- At each period t, the input dataset for the MI procedure will include all placebo patients and those patients from each GWP42003-P arm (implemented separately by arm) that have values at that period.
- The imputation will be realized using the MI procedure with the 'MONOTONE REGPMM' option.

- The imputation model will include daily TSC-associated seizure frequency at baseline and each period up to period t (in chronological order).

Once all missing values at all periods have been imputed, the TSC-associated seizure count for each period will be calculated as:

(Daily frequency for the period × Number of days in the period for the non-imputed period or 14 for an imputed period), rounded to the nearest whole number

The result will be 200 fully imputed datasets ready to be analyzed using the same analysis method as the primary endpoint, producing 200 analysis results.

The estimated ratio, 95% CI and p-value from analyses of the 200 imputed datasets will be combined using PROC MIANALYZE.

To test the robustness of the analysis to the MNAR imputations a tipping point analysis will be performed. This will be conducted by adding or subtracting a sensitivity parameter, $k \times$ standard error of the observed average daily TSC-associated seizure frequency in the placebo arm at each period, to the MNAR imputations only at the corresponding period (where $k = 0, \pm 0.5, \pm 1.0, \pm 1.5$, etc.).

The tipping point analysis will be used to explore the robustness of the estimated treatment difference to the degree of decrease or increase (positive values of k represent decrease and negative values represent increase) in MNAR efficacy from the placebo patients.

The increment in the positive value of k will stop once the overall p-value is greater than 0.05. The decrease in the negative values of k will continue until the overall p-value becomes smaller than the p-value from the primary efficacy analysis, for the corresponding Dose Level.

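### Step 2 of the MNAR imputation selects active-arm patients the wrong way round, so the planned MNAR and tipping-point analysis cannot run as written

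*SAP*

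**What the plan says.** Section 5.5.2.1.1 first fills intermittent gaps by MCMC, which leaves a monotone missing pattern, and then works in two steps.

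- Step 1 completes the placebo arm under MAR.
- Step 2 handles the active arms: "MNAR is assumed for missing values resulting from discontinuation due to any reason or any other monotone missing data". It begins from the completed placebo data: "With the data imputed from Step 1, monotone missing data under the MNAR at period t will be imputed using predictive mean matching method".
- The Step 2 input dataset at period t "will include all placebo patients and those patients from each GWP42003-P arm (implemented separately by arm) that have values at that period".
- Matching means that "missing observations are imputed with an observed value from another patient whose predicated value is close to the predicated value of the patient" who lacks one.
- The Step 2 model contains the daily seizure frequency at baseline and in the successive periods. It has no treatment term.
- The outcome is to be 200 complete datasets, each analysed with the primary model.

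The tipping-point analysis then adds or subtracts k placebo-arm standard errors "to the MNAR imputations only at the corresponding period". It reads k as a decrease or increase "in MNAR efficacy from the placebo patients".

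**The concern.** The selection rule admits the active patients who do not need a value and omits those who do. A programmer must therefore depart from the text to get any imputation, and the text does not say how.

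There are two natural departures. One replaces the observed active patients with the missing ones, so that every donor is a placebo patient. The other adds the missing patients and keeps the observed ones, so that on-treatment active patients become donors. Only the first gives k the meaning that the SAP assigns to it.

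At stake is the evidence that the primary result withstands informative withdrawal. The main SAP plans no other MNAR or tipping-point analysis. Addendum section 2.3.3 reports that withdrawal was higher in each active arm than in placebo, so the ambiguity falls where most values need imputing.

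**Working it through.** The SAP states no figure to reproduce here. The defect is one of logic, and the arithmetic only sizes it.

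**1. Literal reading.** At period t the dataset holds (a) placebo patients, all complete after Step 1, and (b) active patients with a value at t. The number of missing values at t is 0 + 0 = 0. Nothing is imputed, so the 200 complete datasets cannot result.

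**2. Intended reading.** Completing placebo first, then passing all placebo patients into each active arm's imputation, makes sense if placebo is the reference. The tipping-point text also measures departure from placebo patients. The SAP never uses the term placebo-based; that intent is inferred.

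**3. Donor share if observed active patients stay in.** Take 70 per arm (section 3.2), one active arm at a time, and an assumed active withdrawal w. The SAP gives no withdrawal rates.

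Active share of the pool = 70(1 − w) / [70 + 70(1 − w)] = (1 − w)/(2 − w)

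- w = 0.10: 63/133 = 47.4%
- w = 0.20: 56/126 = 44.4%

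**4. Illustrative simulation.** Treatment-to-baseline ratios of 0.85 (placebo) and 0.50 (active) follow from the 15% and 50% reductions in section 3.2. Assumed, not in the SAP: log-normal baseline rates, between-patient log SD 0.5, within-patient log SD 0.25, full effect by the third of eight periods, active-only dropout after period 1 to 7, five nearest donors, 300 replicates. Rates are fractions of baseline over the missing periods.

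| Active dropout | Donors | Active share of donors drawn | Imputed rate | True on-treatment rate, same run |
|---|---|---|---|---|
| 10% | placebo only | 0% | 0.658 | 0.586 |
| 10% | pooled | 52% | 0.605 | 0.575 |
| 20% | placebo only | 0% | 0.655 | 0.604 |
| 20% | pooled | 48% | 0.617 | 0.590 |
| 30% | placebo only | 0% | 0.645 | 0.588 |
| 30% | pooled | 46% | 0.593 | 0.586 |

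Under the literal rule, the active-arm values needing imputation averaged 28.7, 56.2 and 85.7 out of 70 × 8 = 560, and none of them was in the dataset.

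The penalty kept under pooling is the pooled (imputed − true) divided by the placebo-only (imputed − true):

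- 10%: 0.030/0.071, about 41%
- 20%: 0.027/0.051, about 53%
- 30%: 0.007/0.057, about 11%

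Each row used fresh random draws, so these shares are noisy. A second simulation, with all dropout in the first 8 weeks, gave 0.62 (placebo donors), 0.555–0.56 (pooled) and 0.50 (on drug). It kept 0.055/0.12, about 46%.

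**5. Carry-through to the treatment ratio (rough).** Shift = (placebo-only rate − pooled rate) × fraction of active follow-up missing ÷ 0.85.

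- 10%: 0.053 × 28.7/560 ÷ 0.85 = 0.003
- 20%: 0.038 × 56.2/560 ÷ 0.85 = 0.0045
- 30%: 0.052 × 85.7/560 ÷ 0.85 = 0.009
- Second simulation, 10–20% dropout spread evenly over 8 of 16 weeks (about 75% of follow-up missing): 0.065 × 0.75 × (0.10 to 0.20) ÷ 0.85 = 0.006 to 0.011

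The comparison value is a ratio of 0.50/0.85 = 0.59. No calculation was made for the p-value or for the tipping value of k.

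**The case against.** The strongest reply is that a word has dropped out. Reading the bullet as patients with missing values fits everything around it: the split into a MAR and an MNAR step, the limit on which active patients enter, the promise of complete datasets and the tipping-point wording. The literal version would also fail visibly when run. This largely stands as to intent. It does not settle the rule, because the pooled repair also runs and a reader cannot tell which one was used.

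A reader might infer that, under the SAP as written, dropouts borrow the active arm's benefit. The text does not support that: as written nobody is imputed, and borrowing arises only from an unstated addition by the programmer.

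A reader might also infer that nothing else tests active withdrawal. That holds only for MNAR analyses in the main SAP. Addendum section 2.3.3.2 repeats the primary model with withdrawn active patients who had improved set to their baseline rate over 113 days. That is 1.0 of baseline, harsher than the 0.62–0.66 simulated with placebo donors. Section 2.3.3.1 adds time to the 10th and 20th seizure. Both are post hoc and neither has a tipping point, so they do not repair Step 2.

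Finally, this analysis lies outside the testing hierarchy in Table 3 (section 5.5.1). That is correct: no confirmatory test depends on it.

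**Conclusion.** Wrong as written. The Step 2 rule is inverted, and the main SAP's only planned MNAR and tipping-point analysis cannot be executed from its text. This conclusion needs no assumption beyond the wording.

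The consequence for results is conditional. If the program kept observed active patients, the imputation is pooled and near MAR, the bias favours the active arms, and k = 0 is not the placebo-like case. The direction agreed across both simulations. The size did not: between 11% and 53% of the intended penalty remained, depending on dropout and other assumptions and on simulation noise. The resulting shift in the treatment ratio is of the order of 0.01 or less around 0.59, and it rests on withdrawal rates that the SAP does not give. Nothing here shows that the primary result is fragile.

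**What to change.** Replace the input-dataset bullet in Step 2 with wording such as: *At each period t, the MI input comprises every placebo patient (value observed or completed in Step 1) and, from the one GWP42003-P arm being imputed, only the patients whose value at period t is missing (earlier periods observed or already imputed).* All donors are then placebo patients, and k = 0 has the meaning that the tipping-point text gives it.

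Run the tipping-point analysis from these imputations. Confirm and record which rule the program applied. If it kept observed active patients, rerun the MNAR and tipping-point outputs.

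The cost is one sentence and one data filter. If the program already used placebo donors, no result changes; otherwise the MNAR result may become slightly less favourable.
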